Study Population:	Approximately 300 male or female subjects ages 18-85 with a diagnosis of asthma and on biologic therapy will be studied at the University of Michigan in Ann Arbor, MI, USA and approximately 200 male or female subjects over the age of 18 will be studied in the University of Calgary in Calgary, Alberta, CA.
Description of Sites/Facilities	University of Michigan in Ann Arbor, MI, USA is a tertiary academic medical center. Rockyview General Hospital, associated with the
Enrolling Participants:	University of Calgary, Calgary, Alberta, Canada, is tertiary academic medical referral center for patients with severe asthma.
Study Duration:	1.5 years

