2 INTRODUCTION

2.1 STUDY RATIONALE

DISEASE BURDEN IN SEVERE ASTHMA AND THERAPY SELECTION

Asthma is a highly prevalent disease that affects 33 million people in the United States and Canada. The vast majority of asthma patients are well controlled with conventional asthma therapies; however, 10% of patients have severe disease that is associated with significant comorbidity and exposure to high doses of OCS. OCS use increases the odds of developing comorbid diseases such as diabetes, hypertension, cardiac disease and cataracts and is increasingly being recognized as a major contributor to severe asthma costs, making the development of alternative less harmful therapies paramount¹. Fortunately, over the past three years there has been a rapid increase in the number of biologics approved for the management of severe asthma with type II inflammation, which is estimated to be present in up to 60% of this population. The term type II inflammation refers to an increase in the levels of type II cytokines including IL4, IL5 and IL13, which induce pathologic downstream production of IgE and eosinophils. Current clinical practice utilizes surrogate biomarkers, including peripheral and sputum eosinophils, FeNO and total IgE levels, to phenotype patients with severe asthma and guide biologic drug selection. Unfortunately, these surrogates are imperfect and prone to error from multiple sources, especially in the obese².

Unequal Response to Therapy Despite Similar Biomarkers

The response to targeted biologic therapies is heterogeneous despite the use of well-studied biomarkers to select potential responders. Unfortunately, even when patients with a high likelihood of response are selected, 10-15% have complete non-response in all clinical parameters, and only 40% have a robust and complete response to therapy. This is likely related to the presence of overlapping inflammatory pathways, co-morbid eosinophilic diseases that affect response to therapy, possible sub-optimal dosing of drug and the lack of highly specific biomarkers. Precision medicine approaches to severe asthma are in their infancy and the application of complex techniques to help guide therapy are urgently needed. Currently, patients that are partial responders or non-responders to given therapies are switched between available biologics as a means of identifying the best therapy—an inefficient approach that is both time consuming and costly to patients and payers (**Figure 1**).

[figure not shown]

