4 STUDY DESIGN

4.1 OVERALL DESIGN

Over an 18-month period we plan to conduct our study in 3 parts as identified in the study timeline table above.

University of Michigan Cohort Discovery, Database Construction, and Baseline Analysis

We plan to utilize existing data analytic tools at the University of Michigan to search the EMR for eligible patients to include in a retrospective cohort as identified by the inclusion criteria in section 5. We estimate that approximately 300 subjects will meet our initial criteria based on a preliminary search. We will then abstract all available clinical information from the EMR, de-identify it (with coded key stored in a separate, secured location), and enter the resulting coded data into a database. Up to 2 years prior to biologic initiation or CT scan (whichever is earlier) and all post-biologic therapy information will be included. Clinical information we will abstract will include demographic information, heights, weights, comorbid illnesses (coded as malignancy, coronary artery disease, diabetes, stroke/TIA, cirrhosis, and CKD), non-biologic asthma medication dosage and frequency of use (OCS, ICS, SABA, LAMA, LABA, montelukast, zileuton, and theophylline), asthma biologic agent (benralizumab, reslizumab, mepolizumab, omalizumab, and dupilumab) start and (if applicable) end dates as well as reason for end date (coded as ineffective, cost, intolerance/allergy, non-compliance, lost to follow-up, and other), FeNO, ACT scores, serum and sputum eosinophil counts, IgE, pulmonary function test parameters (% predicted), hospital/emergency room/urgent care/unscheduled office visits and phone call encounters for asthma or breathing-related complaints, and subjective clinician assessment of asthma control (independently graded by 2 different clinicians interpretation of EMR data). Each subject will also be assigned a phenotype by the Severe Asthma Research Program criteria¹⁵. If a majority of subjects are missing post-bronchodilator data and unable to be clustered by these criteria, we will instead assign adopted clusters from this paper as follows: Cluster 3-Normal FEV1 ($\geq 68\%$ of predicted), eosinophils (< 200 cells/ μL), FeNO (< 25 ppb), and IgE (< 200 UI/ml) and no evidence of atopy; Cluster 4-Reduced FEV1 ($\leq 68\%$ of predicted) with abnormal elevation of eosinophils, FeNO, or IgE and/or evidence of atopy; Cluster 5--Reduced FEV1 ($\leq 68\%$ of predicted) with normal eosinophils, FeNO, or IgE and no evidence of atopy. We do not expect to have any Cluster 1 or 2 patients in our study but will assign them accordingly if present. We will perform similar abstraction procedures for approximately 200 patients in the University of Calgary cohort, and label the data with a tag for this cohort for analytical purposes.

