
For the purposes of our analysis, we will define baseline measurements as the average of all data obtained in the year prior to biologic initiation or, if only one clinical encounter (defined as an office or emergency room visit) is available in this time period, then the average of the 2 clinical encounters immediately prior to biologic initiation will be used with the time frame noted in the database. In order to assess our primary and secondary outcomes we will use the average of all data from 4 to 18 months after biologic initiation or, if only one clinical encounter is available in this time period, the average of the 2 clinical encounters closest to, but not before 4 months after, biologic initiation. If a second biologic is introduced or the initial biologic choice is

changed, we will use all clinical data prior to the change, even if it is before 4 months of use, then follow the above steps to collect new outcome data on the new drug (see **Figure 4**).

[figure not shown]

Figure 4. Baseline and Response Clinical Data Plan.

Since our interest is primarily in finding the ~15% of patients who do not respond to biologics, we have chosen to include partial and complete responders together in our endpoints in order to isolate the non-responder population. Table 1 below will represent the dichotomization of responders and non-responders for each endpoint using the baseline and post-biologic data as detailed above. An exacerbation will be defined as any hospitalization, urgent care, emergency room, or unscheduled office visit for asthma or a breathing-related complaint or a temporary increase of OCS or ICS dosing for 3 or more days with the intent of the increase to treat acute symptoms. For clinician response, clinical encounter notes will be read and interpreted by 2 independent physicians and graded as detailed in the table. Upon completion of all data abstraction the patient will be de-identified as described in data handling below.

	Responder	Non-responder
Exacerbations	Any decrease from baseline	No change from baseline
Hospitalizations	Any decrease from baseline	No change from baseline
Maintenance oral corticosteroid (OCS) use	Any decrease from baseline	No change from baseline

Change in FEV1	$\geq 5\%$ improvement from baseline	<5% improvement from baseline
ACT score	≥ 1 -point improvement from baseline	No change from baseline
Clinician impression of response to therapy	Any improvement in symptoms from baseline	No change from baseline

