5.2 EXCLUSION CRITERIA

We will exclude patients with a > 10 pack year history of smoking and those with evidence of emphysema on CT imaging due to concerns that concurrent COPD may be attenuating the effects of the biologic. Those with some scattered bronchiectasis thought to be secondary to severe asthma will not be excluded; however, severe bronchiectasis secondary to other causes will be excluded for the same reason. Furthermore, patients who do not have accessible adequate follow-up information (4 or more months from drug initiation with clear documentation of response) will be excluded from the final analysis in part 3 due to an inability to assess response but will be included in the initial analysis to help with cluster identification.

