6.3 IDENTIFICATION OF BIOMARKERS FOR OUTCOMES

To incorporate high-dimensional morphomic parameters to better stratify patients in regard to their probability of complete response, we will leverage the regularization technique in machine learning to select important variables and develop risk predictive models. To be more specific, elastic net regularization will be utilized to address the high dimensional nature of data derived with analytic morphomics. Elastic net consists of a linear combination of L1 (lasso) and L2 (ridge) penalty to address over-fitting and co-linearity, respectively. In addition, to capture potential non-linear effects among variables, we will also apply random forest and gradient boosting, two highly utilized ensemble tree-based methods. Sample splitting will be used to assess model performance. We will evaluate the accuracy of developed predictive models by various performance measures, including Harrell's Concordance index, integrated cumulative area under the curve, and integrated brier score. The final developed predictive model will be evaluated on an independent dataset from the University of Calgary.

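### Section 6.3 leaves sample splitting undefined; one split of about 300 Michigan patients would estimate performance imprecisely, and nested repeated resampling would do better on the same patients

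*Combined protocol and SAP*

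**What the plan says.** Section 6.3 plans elastic net, random forest and gradient boosting on the morphomic measures. For internal assessment it says only "Sample splitting will be used to assess model performance". It then adds: "The final developed predictive model will be evaluated on an independent dataset from the University of Calgary". No other section defines the resampling scheme.

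The sizes come from elsewhere. The Synopsis gives "Approximately 300 male or female subjects ages 18-85 with a diagnosis of asthma and on biologic therapy" at Michigan and "approximately 200 male or female subjects over the age of 18 will be studied in the University of Calgary". Section 4.1 shows that the Michigan figure is an estimate: "We estimate that approximately 300 subjects will meet our initial criteria based on a preliminary search". Under Section 5.2, patients without adequate follow-up "will be excluded from the final analysis in part 3 due to an inability to assess response"; the expected loss is not stated.

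Two places bear on the event rate. Section 2.1 says that among patients selected as likely responders "10-15% have complete non-response in all clinical parameters, and only 40% have a robust and complete response to therapy". Section 4.1 introduces Table 1 with "Since our interest is primarily in finding the ~15% of patients who do not respond to biologics". Table 1 then groups partial and complete responders, endpoint by endpoint, whereas Section 6.3 speaks of the probability of complete response. Section 6.2 pools the Michigan and Calgary cohorts for the CART rules on SARP class and for the clustering.

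**The concern.** Calgary is named separately as the independent dataset, so the ordinary reading of Section 6.3 is that Michigan is divided into a training part and a test part. With a minority outcome, the test part then holds few events, and the reported AUC or concordance has a wide interval. The patients set aside also do not help to build the model.

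The internal estimate is what the investigators will have when they compare the three learners and decide what to take to Calgary. A noisy estimate makes that step depend on the chance of the split. An independent test set already exists, so a second hold-out inside Michigan is a poor use of scarce events when resampling can use all of them.

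**Working it through.** The plan contains no event count, power or precision calculation, so there is no stated figure to reproduce.

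**Inputs from the documents.** Michigan about 300; Calgary about 200; non-response 10-15%; complete response 40%.

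**Assumptions of this check.** Split ratio (70/30 as the main case); true AUC 0.70; analysable Michigan N between 200 and 300.

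**Step 1, events.** Events = N × rate.
- 300 × 0.10 = 30 and 300 × 0.15 = 45 non-responders.
- 300 × 0.40 = 120 complete responders.
- Calgary: 200 × 0.10 = 20 and 200 × 0.15 = 30 non-responders.

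**Step 2, precision of a test-set AUC (Hanley-McNeil).** For a binary outcome the concordance index equals the AUC. With n₁ events, n₀ non-events, a = A/(2−A) and b = 2A²/(1+A):

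Var = [A(1−A) + (n₁−1)(a−A²) + (n₀−1)(b−A²)] / (n₁n₀)

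At A = 0.70, a − A² = 0.0485 and b − A² = 0.0865. For 15% non-response and a 30% test set, n₁ = 13.5 and n₀ = 76.5:

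Var = (0.210 + 12.5 × 0.0485 + 75.5 × 0.0865) / 1032.75 = 0.0071

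SE = 0.084, and the 95% half-width is 1.96 × 0.084 = 0.165.

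| Michigan N | Event rate | Test share | Train / test events | Half-width |
|---|---|---|---|---|
| 300 | 15% | 50% | 22.5 / 22.5 | 0.128 |
| 300 | 15% | 30% | 31.5 / 13.5 | 0.165 |
| 300 | 15% | 20% | 36 / 9 | 0.203 |
| 300 | 10% | 30% | 21 / 9 | 0.199 |
| 240 | 15% | 30% | 25 / 11 | 0.185 |
| 200 | 15% | 30% | 21 / 9 | 0.203 |
| 300 | 40% | 30% | 84 / 36 | 0.113 |

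For comparison, the same formula on all 300 patients gives 0.109, 0.090 and 0.062 at 10%, 15% and 40%. These are optimistic stand-ins for cross-validation, because fold estimates are correlated.

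**Step 3, simulation.** This comparison does not rely on that approximation. It set one 70/30 split against 5-fold cross-validation repeated 5 times. Assumptions: N = 300, 200 correlated predictors of which 10 are informative, best attainable AUC about 0.76, fixed-penalty ridge score, 300 replicates. RMSE is measured against the true AUC of the model fitted to all the data.

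| Event rate | RMSE, one split | RMSE, repeated CV | True AUC, trained on 70% | True AUC, trained on all |
|---|---|---|---|---|
| 15% | 0.087 | 0.059 | 0.581 | 0.595 |
| 40% | 0.068 | 0.042 | 0.595 | 0.612 |

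At 15% the RMSE ratio is 0.059/0.087 = 0.68, a reduction of about one-third. The model gains 0.595 − 0.581 = 0.014. A separate simulation with 300 correlated measures and 15% events gave 0.645 on 210 patients and 0.658 on 300, a gain of 0.013.

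**Step 4, why nesting matters.** With 1000 pure-noise predictors and 45 events in 300 (100 replicates), selecting predictors before forming the folds gave a mean cross-validated AUC of 0.82. Selecting them inside the folds gave 0.48, consistent with no signal.

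**Step 5, Calgary.** With 20-30 events in 200, the half-width at AUC 0.70 is 0.133-0.111.

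**The case against.** The best defence is that the plan never says a single split. Sample splitting can cover k-fold or repeated schemes, and the ratios used here are assumed. This stands: the firm finding is that the scheme is unspecified, and the precision figures are conditional on one split.

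The event count is also open. The 10-15% in Section 2.1 refers to failure on every parameter. In the same population those patients are a subset of those who fail on exacerbations, so the figure is a floor for that endpoint. The 40% for complete response gives 120 events. Losses under Section 5.2 push the other way. A reader might infer that the plan has 45 events; 45 is derived, not stated.

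Other strong readings are tempting but not supported:

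- *The split leaves too few events to train, and cross-validation cures this.* At 15%, training events rise only from 31.5 to 36 per fold in 5-fold cross-validation, and to 45 in the final model. Nor does Section 6.3 rule out a refit on all Michigan patients.
- *Thousands of measures enter the models.* Section 2.2 says that the database can generate thousands; the number used is not given.
- *The imprecision prevents a choice among the three learners.* They would be compared on the same patients, so the comparison is paired, and a single-AUC half-width does not measure it.
- *The selected biomarkers change with the split.* This is plausible but was not calculated.
- *Internal assessment is redundant because Calgary exists.* It allows the learners to be compared before Calgary is used. Only the internal hold-out is unnecessary.
- *The change is free.* Step 4 shows the price of careless nesting.

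**Conclusion.** The point holds in a conditional form and is worth acting on. Section 6.3 does not define its internal validation. If one split is meant, a 30% test set gives a 95% half-width of about 0.17-0.20 at 10-15% non-response, or about 0.11 if complete response at 40% is the outcome. Resampling all Michigan patients is better in both cases. The benefit is mainly a more precise performance estimate; the improvement in the model is only about 0.01 in AUC. Few events against many candidate measures remains the main limit.

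These sizes rest on N of about 300, a true AUC of 0.70, an assumed split ratio and, for the RMSE, the simulation settings above, which used a ridge score and none of the planned learners. The direction of the simulation result matters more than its exact values. The plan must also settle which outcome Section 6.3 models, since its complete response conflicts with the any-response grading in Table 1. Calgary is a clean test only if outputs of the pooled work in Section 6.2 stay out of the outcome models, which the plan does not say.

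**What to change.** Amend Section 6.3 as follows:

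1. Name the modelled outcome, reconcile it with Table 1, and give its expected rate and analysable N.
2. Replace the sample-splitting sentence with repeated stratified k-fold cross-validation (for example 10-fold repeated 20 times), or bootstrap optimism correction, in all Michigan patients with an assessable outcome.
3. Nest scaling, tuning, variable selection and the choice among elastic net, random forest and boosting inside each resample.
4. Refit the chosen procedure on all these Michigan patients, freeze the model, and test it once in Calgary with confidence intervals. State the expected precision there (half-width about 0.11-0.13 at 10-15% non-response).
5. Keep clusters, rules or scaling derived from the pooled cohorts in Section 6.2 out of the outcome models. Phenotypes used as predictors should be derived in Michigan alone.
6. Report how often each measure is selected across resamples.

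If a k-fold scheme was intended from the start, items 2 and 3 simply write it down. The cost is SAP wording, more computing, discipline in nesting, and intervals that are harder to obtain than from a single test set. No extra patients or data are needed.

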7 SUPPORTING DOCUMENTATION AND OPERATIONAL CONSIDERATIONS

7.1 REGULATORY, ETHICAL, AND STUDY OVERSIGHT CONSIDERATIONS

7.1.1 INFORMED CONSENT PROCESS

Both the University of Michigan and University of Calgary sites will apply for exemption of informed consent through their respective local IRBs given the retrospective nature of the study and intent to store all information in a de-identified fashion.

7.1.1.1 CONSENT/ASSENT AND OTHER INFORMATIONAL DOCUMENTS PROVIDED TO PARTICIPANTS

N/A

7.1.1.2 CONSENT PROCEDURES AND DOCUMENTATION

N/A

7.1.2 STUDY DISCONTINUATION AND CLOSURE

This study will be discontinued in approximately 18 months or at completion of the final analysis as detailed above.

7.1.3 CONFIDENTIALITY AND PRIVACY

Both University of Michigan and University of Calgary sites will obtain institutional authorization to share clinical information for the purposes of this study

7.1.4 FUTURE USE OF STORED SPECIMENS AND DATA

All finalized CT and chart data will be stored in a de-identified fashion on University of Michigan servers for future research use.

7.1.6 SAFETY OVERSIGHT

N/A

7.1.7 CLINICAL MONITORING

N/A

7.1.8 QUALITY ASSURANCE AND QUALITY CONTROL

Chart data abstraction will be carried out by research staff and overseen by the principal investigator and co-investigators. For areas where clinical judgement is required (such as identification of an exacerbation or scoring subjective clinical response to therapy), 2 physicians with a pulmonary background will adjudicate the clinical data to ensure quality control.

7.1.9 DATA HANDLING AND RECORD KEEPING

7.1.9.1 DATA COLLECTION AND MANAGEMENT RESPONSIBILITIES

Study oversight will be performed by the principal investigators and the co-investigator and the University of Michigan data analysis team. The study database will be developed on servers managed by MICHRI (the CTSA supported clinical research infrastructure) at the University of Michigan. Web-based data entry and management, as well as the creation and export of study reports for the safety committee will be provided by the University of Michigan under the guidance of the data management core. The study will use the REDCap clinical trial software platform for electronic data capture and clinical data management, as the basis for our custom-designed data entry and management system. Protocols for the transfer of data, with careful attention to data integrity, will be written by experienced programmers and stored in the database. Data collection is the responsibility of the research staff. The investigator is responsible for ensuring the accuracy, completeness, legibility, and timeliness of the data reported.

CT scans anonymization will be performed through existing processes in the analytic morphomic group. Scans will be selected using software that connects directly to the institution's existing PACS system. Once an appropriate scan is identified, it will be downloaded and processed through the morphomic lab's anonymization software. This system removes the patient information stored in each image file's DICOM header, which contains attributes such as name, patient ID, date of birth, etc. All patient identifying data is removed, and a unique identifier (UI) is created and stored in the Patient ID attribute. The UI takes place of the medical record number (MRN) throughout the life of the project. The key connecting this UI with the patient MRN will be maintained and controlled by the project PIs.

7.1.9.2 STUDY RECORDS RETENTION

Data obtained from the study will be retained in a de-identified fashion for a minimum of 3 years after completion of study or longer if required by local regulations.

7.1.10 PROTOCOL DEVIATIONS

Please see additional considerations for anticipated changes to the protocol as described above that may occur once data is obtained.

7.1.11 PUBLICATION AND DATA SHARING POLICY

An explicit goal of this study is to present the primary and related outcomes of this study at Scientific Meetings and to publish, as possible, in peer-reviewed Scholarly Journals to assure dissemination of the findings. The authority to do so resides with the subject investigators and not with any sponsor.

